2. STUDY OBJECTIVES

2.1 PRIMARY OBJECTIVE

The primary objective of the study is to assess the long-term safety and tolerability of ZX008.

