3.3 TREATMENT PERIODS

The duration of participation in the study for an individual subject is expected to be up to 158 weeks, plus a follow-up safety visit 3 and 6 months after the last dose.

- OLE Treatment Period – 36 months (156 weeks)
- Post-Dosing Visit – 2 weeks after study completion or early termination.
- Cardiac Follow-up (ECG and ECHO) – 3 and 6 months after study drug discontinuation for early termination and for those subjects who complete the study.

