6.4 SAFETY ANALYSIS

Safety will be assessed through evaluation of AEs, Laboratory data (hematology, chemistry, urinalysis), vital signs (blood pressure, heart rate, temperature, and respiratory rate), Physical examination, Neurological examination, 12-lead ECGs, Doppler ECHOs, Tanner Staging, BRIEF to measure cognition, and Columbia–Suicide Severity Rating Scale.

All safety analyses will be performed for the SAF population and will be reported for all subjects overall. Select analyses may be repeated by treatment group, for example, treatment-emergent adverse events initiating on or before Visit 2 (Week 2), Visit 3 (Month 1), and Visit 4 (Month 2).

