The original terms used by the investigators in the eCRFs to identify AEs will be coded using the most recent version of the MedDRA implemented by the sponsor at the end of the study.

6.4.1.1 Overview of Adverse Events:

The number and percent of patients with at least one of the following events will be summarized in an overall summary table:

- TEAE
- Serious TEAE
- Related TEAE
- Related serious TEAE
- Severe TEAEs
- Adverse events of special interest
- Deaths

The percentage denominator for the calculation of percentage will be the number of subjects in the SAF population. The above summary will be provided for the OLE treatment period.

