6.4.1.2 Treatment Emergent Adverse Events

The following summaries will display the number and percentage of subjects with an adverse event as well as the corresponding number of events by system organ class (SOC) and preferred term (sorted alphabetically):

- All TEAEs
- All TEAEs occurring in $\geq 5\%$ of subjects
- Serious TEAEs
- TEAEs by Maximum Severity
- TEAEs by prior treatment group, with onset before or up to Visit 1, Visit 2; Visit 3; Visit 4
- Study Drug Related TEAEs

- Study Drug Related TEAEs occurring in $\geq 5\%$ of subjects
- All AEs that lead to premature discontinuation from the study

No inferential statistical methods (i.e., methods that yield p-values) will be used to compare treatment groups on the frequency or severity of AEs.

These summaries will be provided for the OLE treatment period.

Additionally, the following listings will be produced for all enrolled subjects:

- All AEs, events considered to be TEAE will be identified in the listing
- Serious AEs
- AEs that lead to premature discontinuation from the study

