Min, Max	Xx, xx	Xx, xx	Xx, xx	Xx, xx	Xx, xx	Xx, xx
Occurrences per 100 subject years [1]	xxx.xx	xxx.xx	xxx.xx	xxx.xx	xxx.xx	xxx.xx
EEG						
No. of subjects (%)	XX (%)	XX (%)	XX (%)	XX (%)	XX (%)	XX (%)
Number of occurrences for subjects with at least one						
Mean (SD)	XX.X (xx.xx)	XX.X (xx.xx)	XX.X (xx.xx)	XX.X (xx.xx)	XX.X (xx.xx)	XX.X (xx.xx)
Median	XX.X	XX.X	XX.X	XX.X	XX.X	XX.X
Min, Max	XX, xx	XX, XX	XX, xx	XX, XX	XX, XX	XX, XX
Occurrences per 100 subject years [1]	xxx.xx	xxx.xx	xxx.xx	xxx.xx	xxx.xx	xxx.xx
Repeat for the following						
EKG						
ECHO						
PET Scans						
MRI						
X Ray						
CT Scan						

TLF Shells

Zogenix International Limited

ZX008-1503

Surgery						
Lumber Puncture / Spinal Tap						
Other						

mITT = Intent-to-treat;

The mean, median, min and max describe the number of events or procedures per subject for those subjects who had at least one event or procedure.

[1] Occurrence rate is based on the total number of occurrences during the study divided by the total number of subject years of followup for subjects in the column. Multiple occurrences for the same subject are included.

TLF Shells

Zogenix International Limited
ZX008-1503

Programming note: Use the same Table 14.2.8.1 shell to produce

Table 14.2.8.2
Hospitalization and Other Healthcare Resource Utilization to Treat Seizure
mITT Population (Japan)

Table 14.2.9.1
 Number of episodes of status epilepticus (SE)
 mITT Population

	PBO-ZX008 OL (N = XX)	ZX 0.2 - ZX008 OL (N = XX)	ZX 0.5 - ZX008 OL (N = XX)	ZX 0.8 - ZX008 OL (N = XX)	ZX008 OL (N = XX)	De Novo Subjects (N = XX)
Subjects with at Least One episode of status epilepticus reported as AE[1]	XX (XX.X%)	XX (XX.X%)	XX (XX.X%)	XX (XX.X%)	XX (XX.X%)	XX (XX.X%)
Number of seizures reported greater than 10 min[2]						
No. of subjects	XX	XX	XX	XX	XX	XX
Mean per subject	XX.X	XX.X	XX.X	XX.X	XX.X	XX.X
Std. Error	XX.XX	XX.XX	XX.XX	XX.XX	XX.XX	XX.XX
Median	XX.X	XX.X	XX.X	XX.X	XX.X	XX.X
Min	XX	XX	XX	XX	XX	XX
Max	XX	XX	XX	XX	XX	XX
Total unique events: SE as an AE, plus seizures >10 min						
No. (%) of Subjects with at least one event	XX (XX.X%)	XX (XX.X%)	XX (XX.X%)	XX (XX.X%)	XX (XX.X%)	XX (XX.X%)
Age group <6 years	XX (XX.X%)	XX (XX.X%)	XX (XX.X%)	XX (XX.X%)	XX (XX.X%)	XX (XX.X%)
95% Exact CI	(xx.x%,xx.x%)	(xx.x%,xx.x%)	(xx.x%,xx.x%)	(xx.x%,xx.x%)	(xx.x%,xx.x%)	(xx.x%,xx.x%)
Age group ≥6 years	XX (XX.X%)	XX (XX.X%)	XX (XX.X%)	XX (XX.X%)	XX (XX.X%)	XX (XX.X%)

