Programming Note: Include only events whose start date is between Day -30 (inclusive) and Day -1 (inclusive), counting study days from beginning of OLE Treatment period, not core. There will be no De Novo Column for this table.

Use the Table 14.3.1.9.1 shell for

Table 14.3.1.9.1.1

Non-treatment Emergent Adverse Events Starting between Visits 12 and 13 of the Feeder Study, by MedDRA System Organ Class, Preferred Term and Prior Treatment in Feeder Study Safety Population (Japan)

Table 14.3.1.9.2
TEAEs starting in the 1st month of OLE by System Organ Class, Preferred, Term and Prior Treatment in Feeder Study
Safety Population

MedDRA System Organ Class and Preferred Term	Gp1 (N=xx)	Gp 2 (N=xx)	Gp3 (N=xx)	Gp 4 (N=xx)	Gp5 (N=xx)	De Novo Subjects (N=xx)
Subjects with any TEAE starting in the first month.	XX (XX.X%)	XX (XX.X%)	XX (XX.X%)	XX (XX.X%)	XX (XX.X%)	XX (XX.X%)
System Organ Class 1	XX (XX.X%)	XX (XX.X%)	XX (XX.X%)	XX (XX.X%)	XX (XX.X%)	XX (XX.X%)
Preferred Term 1	XX (XX.X%)	XX (XX.X%)	XX (XX.X%)	XX (XX.X%)	XX (XX.X%)	XX (XX.X%)
Preferred Term 2	XX (XX.X%)	XX (XX.X%)	XX (XX.X%)	XX (XX.X%)	XX (XX.X%)	XX (XX.X%)

TEAE = Treatment-Emergent Adverse Event.

Note: A subject with more than one TEAE with the same preferred term is counted once for that term. A subject with more than one TEAE under a system organ class is counted once for that class.

Programming note:

Include only events starting on or after Day 1 up to Day 30 (counting from beginning of OLE Treatment period, NOT Core).

Use same Table 14.3.1.9.2 shell for

Table 14.3.1.9.2.1
TEAEs starting in the 1st month of OLE by System Organ Class, Preferred, Term and Prior Treatment in Feeder Study
Safety Population (Japan)

Programing note: Use the 14.3.1.9.1 shell to produce the following tables. Include only events starting on or after Study Day31 up to Day 60 (counting from beginning of OLE Treatment period, NOT Core)

Table 14.3.1.9.3
TEAEs starting in the 2nd month of OLE by System Organ Class, Preferred Term and Prior Treatment in Feeder Study
Safety Population

Table 14.3.1.9.3.1
TEAEs starting in the 2nd month of OLE by System Organ Class, Preferred Term and Prior Treatment in Feeder Study
Safety Population (Japan)

Programing note: Use the Table 14.3.1.9.1 shell for the following tables. Include only events starting on or after Study Day61 up to day 90(counting from beginning of OLE Treatment period, NOT Core)

Table 14.3.1.9.4

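### AE summaries are crude percentages with no person-time rates, and AE tables by onset interval stop at Day 90 of a 36-month long-term safety study

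*SAP*

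**What the plan says.** Section 2.1 states: "The primary objective of the study is to assess the long-term safety and tolerability of ZX008". Section 3.3 sets the open-label treatment period at 36 months.

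On the AE denominator, Section 6.4.1.1 says: "The percentage denominator for the calculation of percentage will be the number of subjects in the SAF population". The footnotes to the AE table shells in Appendix 1 repeat this. Section 6.4.1.2 adds that the tables will show subjects with an event "as well as the corresponding number of events by system organ class (SOC) and preferred term".

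On timing, Section 6.4.1.2 lists "TEAEs by prior treatment group, with onset before or up to Visit 1, Visit 2; Visit 3; Visit 4", and Section 6.4 identifies Visit 4 as Month 2. The shells for Tables 14.3.1.9.2 to 14.3.1.9.4 cover Days 1-30, 31-60 and 61-90. The instruction for the last of these is: "Include only events starting on or after Study Day61 up to day 90". Table 14.3.1.10.2 separately gives mean time to onset and mean duration from the double-blind phase through the open-label phase, for events in at least 5% of subjects, by mean dose.

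For hospital admissions the SAP does use person-time. The footnote to Table 14.2.8.1 reads: "Occurrence rate is based on the total number of occurrences during the study divided by the total number of subject years of followup".

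**The concern.** A crude percentage rises with time observed. Two columns with the same underlying risk show different percentages if one was followed for longer, and the shorter one looks safer. The AE shells set Groups 1 to 5, all roll-over subjects and de novo subjects side by side. Data-cut reports add further unequal follow-up.

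Late-onset risk is a main reason for running a 36-month extension. Tables by onset interval that end at Day 90 describe early tolerability. They do not show whether events start more or less often in the second or third year.

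**Working it through.** **The plan's own safety figure.** Table 9 (Section 6.1.10) gives the chance of seeing at least 1, 2 or 3 events with n = 270. Exact binomial tails reproduce all 18 cells. At a true rate of 1%:
- at least 1 event: 1 − 0.99^270 = 93.37% (stated 93.4)
- at least 2 events: 75.29% (stated 75.3)
- at least 3 events: 50.72% (stated 50.7)

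Table 9 is not in dispute. Its event rates are proportions of subjects with no follow-up time attached.

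**Coverage of the onset-interval tables.** The last interval ends on Day 90, and the last seizure interval in Table 7a ends on Day 1095. 90 / 1095 = 8.2%.

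**Dependence of a crude percentage on follow-up.** Assume a constant hazard λ per subject-year; the SAP gives no such rate. The expected crude percentage after t years is 1 − exp(−λt).

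| λ (assumed) | 6 months (t = 0.5) | 36 months (t = 3) |
|---|---|---|
| 0.1 | 4.9% | 25.9% |
| 0.2 | 9.5% | 45.1% |
| 0.4 | 18.1% | 69.9% |

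In each row the rate per 100 subject-years is the same in both columns (10, 20 or 40).

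**Share of first onsets that the interval tables would show.** With full 36-month follow-up and constant hazard, the share starting in the first 3 months is (1 − exp(−0.25λ)) / (1 − exp(−3λ)):
- λ = 0.05: 8.9%
- λ = 0.1: 9.5%
- λ = 0.2: 10.8%
- λ = 0.5: 15.1%

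About 85% to 91% of first onsets would fall after Day 90.

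**Where the SAP itself produces unequal follow-up.**
- Section 1 admits entrants to 31 December 2018 with a cut-off of 15 February 2019. The last eligible entrant then has at most 47 days, counting both dates.
- The Japan analysis is triggered when all Japanese subjects have reached at least the Month 3 visit, so subjects who entered earlier will have longer follow-up.
- The exposure shell in Table 14.1.5.1.1 provides categories from under 1 month to 36 months or more.

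**Whether other outputs fill the gap.**
- Table 14.3.1.10.2 covers only events in at least 5% of subjects, uses the earliest occurrence, averages only over subjects who had the event and ignores censoring. A mean of that kind does not give risk in Months 13-24 or 25-36. Its columns are mean dose over the open-label phase. Because everyone starts at 0.2 mg/kg/day, early leavers tend to fall in the low-dose columns with short follow-up.
- Section 6.4.1.2 promises event counts, but the shell for Table 14.3.1.2.1 shows only subjects and percentages, with each subject counted once per term.
- Table 14.1.5.1 reports exposure for Group 1, Group 8, all roll-over subjects and de novo subjects. It does not give exposure separately for Groups 2, 3, 4 and 5, which the AE tables do report.

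**The case against.** The other side has several sound points.

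- A reader might infer that AE timing is tabulated for Months 1-3 alone and that later onset cannot be seen at all. The SAP does not support that. Table 14.3.1.10.2 measures onset from the first ZX008 dose with no cap at Month 3, and Listing 16.2.7.1 gives start and stop days for every event.
- A reader might also infer that the first 90 days are all before full dose. Section 3.2 allows increases after 1 month at intervals of at least 14 days, so some subjects could reach their maximum permitted dose before Day 90.
- The final report follows the last subject's last visit, so it will contain no recent entrants; short follow-up there means leaving early. The 2018 interim shows one combined column, the 120-day outputs leave de novo subjects out, and Japan has its own tables.
- Follow-up by group is not given. For Groups 1 to 3, which come from the arms of the same randomised studies, it may be similar.
- AE results are descriptive, with no p-values between groups, and crude incidence with exposure reported separately is a legitimate presentation.

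These points limit the concern without removing it. Descriptive columns are still read side by side. A conditional mean and a listing do not show risk by period. The exposure table does not match the AE columns.

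**Conclusion.** The point holds as a gap in presentation and interpretability. It is not a testing error. Two facts rest on the SAP alone: no AE table has a person-time or at-risk denominator, and AE tables by onset interval cover 8.2% of the planned period.

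The comparability problem applies wherever columns differ in time on drug: the Japan interim, early leavers, and possibly the de novo and mean-dose groups. Its size is not known. The contrast of 9.5% with 45% assumes 0.2 first events per subject-year, a constant hazard, and 6 versus 36 months of follow-up; none of these is a figure from the SAP. The estimate that 85% to 91% of first onsets fall after Day 90 assumes a constant hazard of 0.05 to 0.5 per subject-year and complete follow-up.

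This is a cheap improvement: it would let the report describe late-onset risk and read unequal columns fairly.

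**What to change.** 1. In Tables 14.3.1.1, 14.3.1.2.1, 14.3.1.4 and 14.3.1.8, keep the crude percentages and add, for each column, subject-years and the first-event rate per 100 subject-years. Stop each subject's time at the first event or at the end of observation. Table 14.2.8.1 already applies a person-time rate to hospital admissions.
2. Add one AE table by onset interval to Month 36: Months 1-3, 4-12, 13-24 and 25-36. With the Table 7a boundaries these are Days 1-90, 91-360, 361-730 and 731-1095. Use subject-years at risk within each interval as the denominator.

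The cost is extra programming and longer tables. No new data are needed, because dosing dates and AE start dates are already collected.

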6.4.2 Adverse Events of Special Interest (AESI)

As per ICH guidance (E2F Development Safety Update Report [2011]), the Sponsor has identified the following AESIs for the ZX008 program.

Table 12 Adverse Events of Special Interest:

Metabolic/Endocrine
1. Elevated prolactin level $\geq 2x$ above the upper limit of normal (ULN)
2. Hypoglycemia – serum blood glucose more than 20% below the glucose level on Study Day -1 value or more than 10% below LLN (reference range 60 – 140 mg/dL)
Neuropsychiatric
1. Suicidal thoughts, ideation or gestures

LLN = lower limit of normal; ULN = upper limit of normal

The following summary tabulations will be provided to explore the AEs of special interest:

- AEs with decreased appetite or hypophagia

Adverse events of special interest will be summarized overall, and by treatment group, ZX008 combined and overall by system organ class and preferred term for the OLE treatment period.

All adverse events of special interest will be listed separately.

6.4.3 Physical Examination

A complete physical examination will be performed at Visit 1 and EOS/ET visit (Visit 16), and at the Cardiac follow-up visits (Visit 17 and 18). An abbreviated physical exam is performed at Day 15 (Visit 2), Visit 3 through Visit 16 (Days 30, 60, 90, 180, 270, 365, 455, 545, 635, 725, 815, 905 and 995)

All physical examination results will be presented in a subject data listing, including the description of abnormalities.

6.4.4 Neurological Examination

A complete neurological examination will be performed at baseline (OLE) Visit (Visit 1) and at EOS / ET (Visit 16).

All neurological examination results will be presented in a subject data listing, including the description of abnormalities.

6.4.5 Vital Signs, Weight, and BMI

Vital signs data including blood pressure, heart rate, temperature, respiratory rate, weight, and BMI will be documented for subjects during study Visits 1 through Visit 16 (EOS/ET).

The actual value and change from baseline (OLE) to each on-study evaluation time point will be summarized for vital signs and weight overall and by treatment group. Vital signs, weight and BMI data will be presented for each patient in a data listing.

A listing of subjects with Potentially Clinical Significant vital sign results will be provided. In this listing, those values outside the sponsor defined alert ranges will be marked and further available details about clinical relevance and diagnosis will be added.

Descriptive statistics will be provided for weight over time at baseline (OLE), and every 3 months during the OLE treatment period, for all subjects in the safety population. For the same time periods, the percent of subjects who lost at least 7% or 10% of their body weight during OLE when compared to baseline (OLE) will be summarized. Similarly, the percent of subjects who gained 7% or 10% of their body weight during OLE when compared to baseline (OLE) will be summarized. For subjects who lost at least 7% of their body weight, the number who achieved a recovery to their baseline (OLE) weight, and the duration of time to recovery, will be summarized. Recovery will be defined as achieving a weight, after the $\geq 7\%$ reduction, which is at least 99% of the baseline (OLE) weight at two separate, consecutive assessments. The number of days until weight recovery will be determined using the date of the first date where the weight loss was observed and the first date where the subject's weight had recovered to, and maintained for at least two consecutive study visits, at least 99% of the baseline (OLE) weight. A similar analysis of 5% weight loss and weight gain will be conducted.

In addition, weight will be summarized by age group (2-<4; 4-<6; 6 to<12; and ≥ 12 years).

A scatterplot will plot height and age for subjects at the end of the OLE period.

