3.2 TREATMENTS

Subjects in the double-blind studies Z008-1501, -1502, and cohort 2 of 1504 who enter Study ZX008-1503 would have transitioned to 0.2 mg/kg during the transition period (between Visits 12 and 13), as described in the 1501 and 1502 Clinical Study Protocols Section 5.5.5, and 1504 Sections 5.5.6 and 5.5.7. Subjects entering from Cohort 1 in Study ZX008-1504 will enter a transition period at a fixed dose of ZX008 0.2 mg/kg/day for up to 24 additional weeks.

In Study ZX008-1503, during the OLE Treatment Period, all subjects will be treated initially with 0.2 mg/kg/day for 1 month to assess effectiveness of this dose in all study subjects. After 1 month at a dose of 0.2 mg/kg/day, the investigator may adjust the dose of each subject based on effectiveness and tolerability. Subjects whose condition worsened relative to their status at the end of the double-blind feeder study could request permission to increase to 0.4 mg/kg/day (max 30mg) after approximately 2 weeks on the 0.2 mg/kg dose. Dose changes should be made in increments of 0.2 mg/kg/day, to a maximum of 0.8 mg/kg/day but not to exceed total dose of 30 mg/day. Dose increases should not occur earlier than every 14 days at each dose level. For subjects in Study ZX008-1504 Cohort 2, the dose titration schedule is 0.2 mg/kg/day, to 0.4, to 0.5 not to exceed 20 mg/day. Dose increases may only occur after a review of the diary and reported AEs, and if, in the investigator's opinion, seizure frequency, severity, and/or duration indicates a change in medication regimen is warranted. Dose decreases for tolerability can occur at the investigator's discretion, in dose amounts and frequency appropriate for the situation. ZX008 dose adjustments outside of these parameters should be discussed with the Medical Monitor prior to initiation.

Effectiveness and safety data will be provided for all subjects treated with ZX008. Data will be summarized by subjects' treatment group in their previous study.

The treatment groups that may be used to summarize the results of the final analysis are presented in Table 1. Groups 1 to 5 are the basic treatment groups.

Table 1. Treatment Groups in Study ZX008-1503 According to Treatment in Feeder Study

Name of Treatment Group	Treatment Group Code	AED Treatment from Feeder study	Feeder Study(s)	Approximate Total Number of subjects at Final Analysis

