PBO-ZX008 OL	1	Placebo in feeder study along with any protocol-approved background AED combination; no active ZX008	1501, 1502, 1504 Cohort 2	120
ZX 0.2 – ZX008 OL	2	Any protocol-approved background AED combination; plus, ZX008 0.2 mg/kg/day max 30 mg	1501, 1502	80
ZX 0.8 – ZX008 OL	3	Any protocol-approved background AED combination; plus, ZX008 0.8 mg/kg/day max 30 mg	1501, 1502	80
ZX 0.5 – ZX008 OL	4	Protocol-approved background regimen including STP + VPA and/or CBZ; plus ZX008 0.5 mg/kg/day max 20 mg	1504 Cohort 2	40
PK - ZX008 OL	5	Protocol-approved background regimen including STP + VPA and/or CBZ; plus ZX008 0.5 mg/kg/day max 20 mg	1504 Cohort 1	18
ZX DBA – ZX008 OL	6 (Groups 2-4)	Any protocol-approved background regimen, plus ZX008 at any protocol-approved dose – DB Studies only		200
ZX DB – ZX008 OL	7 (Groups 1-4)	Any protocol-approved background regimen at any protocol-approved dose – DB Studies only		320
ZX – ZX008 OL	8 (Groups 2-5)	Any protocol-approved background regimen, plus ZX008 at any protocol-approved dose – All studies		218
ZX008 OL	9 (Groups 1-5)	Any protocol-approved background regimen at any protocol-approved dose – All studies		338
De Novo Subjects	10	N/A	N/A	TBD

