6.1.4 Definitions

6.1.4.1 Baseline (Core)

For de novo subjects, the baseline (core) is undefined. For other subjects, the baseline (core) is defined as follows.

For effectiveness endpoints (excluding seizure), the baseline (core) will be defined dependent on their core study. For subjects from ZX008-1501, ZX008-1502, or ZX008-1504 Cohort 2, baseline (core) is the last value prior to randomization in the preceding double-blind study. For subjects from ZX008-1504 Cohort 1, baseline (core) is the last value prior to the start of PK dosing and assessments. For De Novo subjects, the baseline is the last value prior to dosing in ZX008-1503.

For all subjects in Study ZX008-1501, Study ZX008-1502, or Study ZX008-1504 Cohort 2, the baseline (core) period is equivalent to the core study pre-randomization period, i.e., the approximately 42-day span just prior to randomization and start of treatment in the core study. The baseline (core) seizure frequency will be based on the information collected from their daily diaries during the baseline period (lasting approximately 42 days).

For subjects from Study ZX008-1504 Cohort 1 the baseline (core) for efficacy rating scales (e.g. questionnaires) will be the last rating prior to start of dosing in the Core Study. Baseline seizure frequency for Study ZX008-1504 Cohort 1 will not be calculated.

6.1.4.2 *Baseline (OLE)*

Baseline (OLE) value for the Open-label treatment period is defined as the last assessment on or before the start of the OLE period. In most cases, (though not seizure frequency) this will be the value obtained at Visit 1 (Study Day 1) of Study ZX008-1503.

Thus, Baseline (OLE) lab, vital signs, ECG, ECHO, assessments refer to the assessments obtained on this day, as does Baseline (OLE) value for effectiveness endpoints with the exception of seizures.

For de novo subjects, the baseline (OLE) seizure frequency will be based on the information collected from their daily diaries during the baseline period (lasting approximately 28 days) prior to first dose in ZX008-1503.

6.1.4.3 *Open-Label Extension (OLE) Treatment Period*

The OLE Treatment Period covers the 36 months during which subjects will receive open label treatment with ZX008.

For each subject, OLE day 1 (OLED1) is the subject's first day of dosing in the OLE period. Study day for 1503 begins with OLED1.

6.1.4.4 *Post-dosing Period*

The Post-dosing Period begins immediately at the end of OLE Treatment Period and extends for 2 weeks.

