Name of Treatment Group	Treatment Group Code	Description	AED Treatment from Feeder study	Feeder Study(s)	Approximate n
PBO-ZX008 OL	1	Placebo arms in all studies	Placebo in feeder study along with any protocol-approved background AED combination; no active ZX008	1501, 1502, 1504 Cohort 2	120
ZX 0.2 – ZX008 OL	2	0.2 arm in DB Studies	Any protocol-approved background AED combination; plus, ZX008 0.2 mg/kg/day max 30 mg	1501, 1502	80
ZX 0.8 – ZX008 OL	3	0.8 arm in DB studies	Any protocol-approved background AED combination; plus, ZX008 0.8 mg/kg/day max 30 mg	1501, 1502	80
ZX 0.5 – ZX008 OL	4	Active arm in 1504 cohort 2	Protocol-approved background regimen including STP + VPA + CBZ; plus ZX008 0.5 mg/kg/day max 20 mg	1504 Cohort 2	40
PK – ZX008 OL	5	Cohort 1 PK Study - Open label study		1504 Cohort 1	40
Summary Treatment Groups¹					
ZX DBA – ZX008 OL	6 (Groups2-4)	All Active arms in the DB studies	Any protocol-approved background regimen, plus ZX008 at any protocol-approved dose – DB Studies only	1501, 1502, 1504 Cohort 2	200
ZX DB – ZX008 OL	7 (Groups1-4)	All subjects in randomized double-blind (DB) studies	Any protocol-approved background regimen at any protocol-approved dose – DB Studies only		
ZX – ZX008 OL	8 (Groups2-5)	All Active arms	Any protocol-approved background regimen, plus ZX008 at any protocol-approved dose – All studies	1501, 1502, 1504 Cohort 1, 1504 Cohort 2	240
ZX008 OL	9 (Groups1-5)	All Subjects in 1503 excluding de novo subjects	Any protocol-approved background regimen at any protocol-approved dose – All studies	1501, 1502, 1504 (both cohorts)	360
De Novo Subjects	10		Subjects entering 1503 who had not participated in any of the core studies	None	35

Notes:1: Subjects in 1504 cohort 1 do not have a pre-study treatment baseline for seizures and are not included in analyses requiring baseline (Core) seizure frequency.

Analysis Summary types

Type	Treatment By Groups (Codes as above)
A	1, 2, 3, 4,5,9, 10
B	1, 8, 9, 10
C	1, 6, 7, 10

TLF Shells

Zogenix International Limited
ZX008-1503

NOTES:

The TFL shells provided are for the final study report. For the interim analysis, please note the following:

Programming Prioritization for Interim Analysis, 2018

Provide summaries for ZX008 OL (Group 9), i.e., "All Subjects" column only

- 1 = High priority -
- 2 = Medium Priority
- 3 = Low Priority

LIST OF TABLES, FIGURES AND LISTINGS FOR FINAL REPORT

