Note: Time windows are specified in the statistical analysis plan. In the event of 2 or more assessments in the interval, the assessment completed closest to the target time point are assessed. For the last assessment, the last non-missing value observed.

[1] Percentages are based on the number of subjects with a baseline weight and a weight at the visit meeting the criteria noted in the row.

[2] A subject recovered, if they had a weight recorded after the visit being summarized that was within 1% of the baseline body weight at 2 consecutive visits. Percentages are based on the number of subjects who had the 7%/10% weight loss and had a value meeting the criteria noted in the row.

Programming Notes: Use the Table 14.4.1.5 shell for the following tables.

Table 14.4.1.5.1

Weight Summary (Lost/Gain \geq 7% or \geq 10%) during the Open-Label Study Period

Safety Population (Japan)

Table 14.4.1.6

Weight Summary (Lost/Gain \geq 7%, or \geq 10%) during the Open-Label Study Period by Concomitant Topiramate

Safety Population

Table 14.4.1.6.1

Weight Summary (Lost/Gain \geq 7%, or \geq 10%) during the Open-Label Study Period by Concomitant Topiramate

Safety Population (Japan)

Programming notes: Repeat Table 14.4.1.5 for 14.4.1.6 and 14.4.1.6.1 by subset by (a) subjects on concomitant topiramate, and (b) subjects not on concomitant topiramate.

Programming note: Use the Table 14.4.1.5 shell but only present for 5% to produce the following tables.

Table 14.4.1.7

Weight Summary (Lost/Gain \geq 5%) during the Open-Label Study Period

Safety Population

Table 14.4.1.7.1

Weight Summary (Lost/Gain \geq 5%) during the Open-Label Study Period

Safety Population (Japan)

Table 14.4.1.8

Weight Summary (Lost/Gain $\geq 5\%$) during the Open-Label Study Period by Concomitant Topiramate
Safety Population

Table 14.4.1.8.1

Weight Summary (Lost/Gain $\geq 5\%$) during the Open-Label Study Period by Concomitant Topiramate
Safety Population (Japan)

Table 14.4.4.1
 Tanner Staging by Age Group for Boys
 Safety Population

Age Group	Visit [1]	Tanner Stage	Gp1 (N = XX)	Gp2 (N = XX)	Gp3 (N = XX)	Gp4 (N = XX)	Gp5 (N = XX)	Gp9 (N = XX)
<7years	Baseline (OLE)(Day 1)	Stage I	XX (XX.X%)	XX (XX.X%)	XX (XX.X%)	XX (XX.X%)	XX (XX.X%)	XX (XX.X%)
		Stage II	XX (XX.X%)	XX (XX.X%)	XX (XX.X%)	XX (XX.X%)	XX (XX.X%)	XX (XX.X%)
		Stage III	XX (XX.X%)	XX (XX.X%)	XX (XX.X%)	XX (XX.X%)	XX (XX.X%)	XX (XX.X%)
		Stage IV	XX (XX.X%)	XX (XX.X%)	XX (XX.X%)	XX (XX.X%)	XX (XX.X%)	XX (XX.X%)

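### Weight recovery is defined one way in SAP Section 6.4.5 and another in the table footnote, and weight change is measured only from Baseline (OLE), without reference to expected growth

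*SAP*

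**What the plan says.** Section 6.4.5 plans "the percent of subjects who lost at least 7% or 10% of their body weight during OLE when compared to baseline (OLE"), the corresponding gain percentages, and a similar 5% analysis. For subjects who lost at least 7%, it counts recovery as a weight "which is at least 99% of the baseline (OLE) weight at two separate, consecutive assessments". Days to recovery run from the date the loss was first observed. The same 99% floor appears again in the sentence on days to recovery, and neither sentence sets an upper limit.

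Note [2] under the shell of Table 14.4.1.5 counts a subject as recovered if a weight after the visit being summarised was "within 1% of the baseline body weight at 2 consecutive visits". Programming notes reuse this shell for Tables 14.4.1.5.1, 14.4.1.6, 14.4.1.6.1, 14.4.1.7, 14.4.1.7.1, 14.4.1.8 and 14.4.1.8.1, which makes eight tables in all.

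Baseline (OLE) (Section 6.1.4.2) "is defined as the last assessment on or before the start of the OLE period". By Section 3.2, entrants from the double-blind studies "would have transitioned to 0.2 mg/kg during the transition period (between Visits 12 and 13"), with no exception for placebo, and Study 1504 Cohort 1 entrants "will enter a transition period at a fixed dose of ZX008 0.2 mg/kg/day for up to 24 additional weeks". De novo subjects are described in the shells as "Subjects entering 1503 who had not participated in any of the core studies".

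**The concern.** Long-term safety is the primary objective, and weight and appetite loss have their own tables. Three features affect how those tables can be read.

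- **Two recovery rules.** A programmer working from the shell would apply a two-sided band where the SAP text sets only a floor. The children who regain fastest would then be the likeliest to be counted as not recovered. The two rules also start the search at different points: the first observed loss in the text, the visit being summarised in the note. The block for any visit in the OLE has no single visit to start from.
- **Reference weight.** For core-study subjects, weight already lost on ZX008 before OLE entry lies outside every weight-change summary, and a return to the reduced weight counts as recovery.
- **No allowance for growth, and conditional days to recovery.** A percent-loss criterion in kilograms does not register a child who stops gaining over 36 months. Days to recovery are summarised only in those who recovered.

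**Working it through.** The SAP states no numerical target for weight; these analyses are descriptive. Its only probability table (Table 9, n = 270) reproduces by exact binomial, for example 1 − 0.99^270 = 93.4% for at least one event at a 1% rate, but it has no bearing here.

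**1. The two recovery rules**

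Inputs: the floor of 99% (Section 6.4.5); the literal band 99–101% (note [2]); visit days 30, 60, 90, then about every 90 days (Tables 4 and 5).

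The band is 2% of baseline wide. For two consecutive visits to fall inside it under steady regain, the rate cannot exceed 2% ÷ (visit gap in years):

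- 90-day gap: 2% ÷ (90/365.25) = 8.1% of baseline per year
- 30-day gap: 2% ÷ (30/365.25) = 24.4% per year

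A simulation on the SAP visit days shows how far the counts can separate. It assumes a lowest weight of 88–93% of baseline reached at day 60, 90, 180 or 270, linear regain, and measurement error with the SD shown. Both rules are searched from the first observed loss of at least 7%.

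| Assumed regain per year | At least 99%, no error | Within 1%, no error | At least 99%, SD 1% | Within 1%, SD 1% |
|---|---|---|---|---|
| 3% | 19% | 19% | 17% | 13% |
| 5% | 95% | 60% | 91% | 43% |
| 8% | 100% | 2% | 100% | 23% |
| 10% | 100% | 0% | 100% | 13% |

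The rules nearly agree when regain is slow and part sharply from about 5% per year.

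**2. Exposure before Baseline (OLE)**

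Table 1 gives Groups 2–5 ("plus ZX008 at any protocol-approved dose – All studies") as 80 + 80 + 40 + 18 = 218 of 338, or 64.5%. These subjects had active drug in the core study itself. The other 120 (former placebo) had only the transition period. All 338 therefore have a reference weight taken after some ZX008 exposure. The group table repeated with the shells gives 240 of 360 and about 35 de novo subjects. De novo subjects, whose baseline precedes drug, are then 35/(338 + 35) = 9.4% or 35/(360 + 35) = 8.9% of the total.

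**3. No weight gain for 36 months**

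The SAP gives no growth rate, so expected gain g per year is assumed. The shortfall against expected weight is 1 − w/(1 + g)³, where w is final weight as a fraction of baseline.

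| Assumed g | No change (w = 1) | At the recovery floor (w = 0.99) |
|---|---|---|
| 3% | 8.5% | 9.4% |
| 5% | 13.6% | 14.5% |
| 10% | 24.9% | 25.6% |
| 15% | 34.2% | 34.9% |

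In the first case the loss tables show 0% loss. In the second, a child who had earlier lost 7% and then held 99% at two consecutive assessments is counted as recovered.

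**4. Days to recovery**

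The shell gives mean, SD, median, minimum and maximum. A subject who has not recovered has no value and drops out, and a loss first seen at the last visit cannot be followed by two later assessments. The summary is therefore short if read as the time to recovery of everyone who lost weight.

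**The case against.** The footnote may have been meant as no more than 1% below baseline, in which case the two rules coincide. That is plausible, and the body text is unambiguous, but tables are programmed from the shell, so the wording still has to be reconciled.

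A reader might infer that growth failure would go unseen. The SAP does not support that. It plans observed weight and change by visit, weight in four age bands, rows for gains of 5%, 7% and 10%, an end-of-study height-by-age scatterplot, a listing of percent change in weight and BMI, growth laboratory tests and Tanner staging. A child with no gain is absent from the gain rows and contributes zero change to the age-band table. What stands is narrower: none of these expresses weight relative to what is expected for age and sex.

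A reader might also take 64% as the share of subjects with an on-drug reference weight. It is the share of core-study subjects on active drug in the core study; by Section 3.2 the former placebo subjects had also moved to ZX008 by OLE entry, while de novo subjects had not.

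Baseline (OLE) is a stated convention, also used for laboratory data, ECG and ECHO, and change during the extension is a fair question. Core-period weight change may be reported with the core studies or the integrated safety summary, which are not shown. A Baseline (Core) comparison is therefore an addition to the plan and does not correct an error.

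Finally, the number recovered is printed directly above days until recovery, so the conditioning is visible. The objection to the summary is about interpretation, and no size can be put on it from the document.

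**Conclusion.** The contradiction in the recovery definition holds and should be resolved before the weight tables are produced. Read literally, note [2] fails children who regain beyond 101% of baseline, and with 90-day visits steady regain above about 8% per year cannot qualify. In the simulation at 5% per year without error, counted recovery falls from 95% to 60%. Those percentages rest on assumed regain and error rates; the 8.1% limit rests only on the band width, the visit gap and steady regain without measurement error.

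It also holds that all weight-change, loss, gain and recovery summaries start from Baseline (OLE), after ZX008 exposure for every core-study subject, and that none is standardised for age and sex. The 8.5–34% shortfall is an illustration under assumed growth of 3–15% per year. It is not an estimate for this population, which includes older adolescents and de novo adults up to 35 years. A reader might go further and hold that z-scores must be the main weight summary; that would be a preference, and the document gives no ground for more than a supplement.

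**What to change.** - **Required.** Replace note [2] of Table 14.4.1.5 with the Section 6.4.5 rule (a floor of 99% of Baseline (OLE) weight at two consecutive assessments, no upper limit), and start the search at the first observed loss, as the text does. All eight tables inherit the change. Cost: one footnote.
- **Suggested.** Repeat the 5%, 7% and 10% loss tables against Baseline (Core) for core-study subjects, with de novo subjects shown separately against their pre-dose weight.
- **Suggested.** Add a supplementary summary of change in weight, height and BMI z-scores, limited to subjects within the age range of a pre-specified growth reference. State which reference applies to the Japanese subgroup.
- **Suggested.** Report time to recovery by Kaplan-Meier among all subjects with the loss, censoring those not recovered at their last weight.

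Weight, height, age and sex are already collected. The cost is a few extra tables and agreement on a growth reference.
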